16.5 Evaluation of Toxicity

For the safety analysis, all enrolled patients who receive at least one dose of cabozantinib and nivolumab will have information collected on adverse events, which will be summarized by severity as assessed by the Common Toxicity Criteria for Adverse Events (CTCAE), v. 5.0 and relationship to study drugs.

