5.3 Agent Administration

On days when Nivolumab and Cabozantinib are administered on the same day (i.e. Day 1 of each cycle) the order of agent administration does not matter.

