5.3.2 Cabozantinib administration

Cabozantinib will be administered orally, once daily for 28 days at a dose of 40 mg. Cabozantinib should be taken 2 hours after a meal (water is permitted) with a full glass of water (8oz/240mL). Participants should continue to fast for 1 hour after taking cabozantinib. Participants will be provided with dosing instructions, a drug diary and a sufficient supply of cabozantinib for continuous daily dosing. Cabozantinib should be dosed on an outpatient basis even on days where Nivolumab and Cabozantinib are dosed together (i.e. Day 1 of each cycle). While taking Cabozantinib, participants should avoid consumption of grapefruit and Seville oranges. Cabozantinib should not be crushed, chewed, or dissolved in water.

Subjects should be instructed to take their cabozantinib dose at approximately the same time every day. If a subject misses a dose, the dose may be taken later only if it is within 12 hours of when the missed dose should have been taken. The missed dose should not be made up if it is within 12 hours of the next scheduled dose.

Management and dose modifications associated with the above adverse events are outlined in Section 6.

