7.3 Adverse Event Reporting

- 7.3.1 In the event of an unanticipated problem or life-threatening complications treating investigators must immediately notify the Overall PI.
- 7.3.2 Investigators **must** report to the Overall PI any adverse event (AE) that occurs after the initial dose of study treatment, during treatment, or within 30 days of the last dose of treatment on the local institutional SAE form.
- 7.3.3 DF/HCC Adverse Event Reporting Guidelines

Investigative sites within DF/HCC will report AEs directly to the DFCI Office for Human Research Studies (OHRS) per the DFCI IRB reporting policy.

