7.4 Routine Adverse Event Reporting

All Adverse Events **must** be reported in routine study data submissions to the Overall PI on the

toxicity case report forms. **AEs reported through expedited processes (e.g., reported to the IRB, FDA, etc.) must also be reported in routine study data submissions.**

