7.5 Expedited Reporting to BMS

All SAEs that occur following the subject's written consent to participate in the study through 100 days of discontinuation of dosing must be reported to BMS Worldwide Safety, whether related or not related to study drug. If applicable, SAEs must be collected that relate to any later protocol-specified procedure (eg, a follow-up skin biopsy). Although pregnancy, overdose, potential drug-induced liver injury (DILI), and cancer are not always serious by regulatory definition, these events must be handled as SAEs.

Any component of a study endpoint that is considered related to study therapy should be reported as an SAE (eg, death is an endpoint, if death occurred due to anaphylaxis, anaphylaxis must be reported).

All SAEs must be reported to BMS within 24 business hours of the awareness of the event. SAEs must be recorded on a Medwatch Form 3500A.

SAE Email Address: [contact]

SAE [contact]

If only limited information is initially available, a follow-up report is required and should include the same investigator term(s) initially reported.

If an ongoing SAE changes in its intensity or relationship to study drug or if new information becomes available, a follow-up SAE report should be sent within 24 hours of awareness to BMS (or designee) using the same procedure used for transmitting the initial SAE report.

All SAEs should be followed to resolution or stabilization.

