16.3 Analysis Plan

The primary endpoint is the objective response rate (ORR). We will calculate the frequency and percentage of responses. The point estimate of the ORR with a 9% confidence interval based on the exact binomial distribution will be presented.

With a sample size of 35, if the observed ORR is 30%, we will estimate the 95% confidence interval for the ORR to be 14.8% to 45.2%.

Below is a table for the 95% CIs corresponding to varying observed ORR

	95% CI
15%	3.2% to 26.8%
20%	6.8% to 33.3%
30%	14.8% to 45.2%
40%	23.8% to 56.2%

The secondary endpoints are safety, response rate according to immune-related response criteria, duration of response, progression free survival (PFS), and overall survival (OS) for patients with advanced carcinoid tumors treated with the combination of cabozantinib and nivolumab.

Safety will be assessed by analysis of adverse event (AE) and toxicity data. AE and toxicity data, including laboratory values, will be graded using CTCAE version 5.0. Tabulations of toxicities will be provided by organ system and attribution.

Response rate according to immune-related response criteria will be analyzed using the same method for ORR. Duration of response will be summarized using mean, standard deviation, median, and inter-quartile range.

Progression free survival and overall survival will be defined from time of randomization to time of progression or date of death, respectively. Any patients who have not died by the analysis cut-off date or are lost to follow up will be censored at their last date of contact. Any patient that withdraws consent for follow up will be censored on the date of withdrawal of consent. Kaplan-Meier method will be employed to obtain survival estimates and median survival times will be provided. Greenwood's formula will be used to construct 95% confidence intervals around these estimates.

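### Read literally, Section 16.5 leaves a patient who received only one of the two drugs out of the safety summary, although Section 7 records that patient's adverse events from the first dose

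*Combined protocol and SAP*

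**What the plan says.** Section 16.5 is the only place where the documents define who is in the safety analysis. It states that "all enrolled patients who receive at least one dose of cabozantinib and nivolumab will have information collected on adverse events", and that these events will be summarized by severity and by relationship to the study drugs.

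Section 16.3 describes the method: "Safety will be assessed by analysis of adverse event (AE) and toxicity data", with tabulations by organ system and attribution. It names no population.

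Section 7 sets the collection rules, and none of them depends on having received both drugs:

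- Section 7.3.2 requires investigators to report "any adverse event (AE) that occurs after the initial dose of study treatment, during treatment, or within 30 days of the last dose" of treatment.
- Section 7.4 requires all adverse events to be "reported in routine study data submissions to the Overall PI", on the toxicity case report forms.
- Section 7.5 requires that all serious events from written consent "through 100 days of discontinuation of dosing must be reported to BMS Worldwide Safety".
- Section 7.6 has serious events documented once cabozantinib has started, with no nivolumab condition.

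On dosing, Section 5.3 says that when both agents fall on the same day "the order of agent administration does not matter". Section 5.3.2 adds: "Cabozantinib should be dosed on an outpatient basis even on days where Nivolumab and Cabozantinib are dosed together". The Study Calendar (Section 10) starts both agents on Cycle 1 Day 1 and allows 3 days either side of a scheduled date. The table in Section 6.24 continues cabozantinib at every grade of infusion reaction.

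**The concern.** A safety set normally contains everyone exposed to any study drug. A set that requires both drugs drops patients who stopped after the first one, and early toxicity is one possible reason for stopping. Such an exclusion could be related to the outcome being summarized, and it would remove the event from the numerator and the patient from the denominator.

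The wording matters more here than in a large trial. There are at most 35 patients. Section 16.1 says the interim look at 18 is partly to assure tolerability, but Section 16.4 gives only a response rule. Tolerability will therefore be judged from the descriptive adverse event summary, so the population behind that summary should be unambiguous. As it stands, one programmer could build a both-drugs set from 16.5 and another an any-drug set from Section 7 and 16.3.

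**Working it through.** No figure in the documents depends on the safety set, so there is nothing to reproduce. The check compares the texts and then bounds the effect.

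**Step 1: who is in.** Consider a patient who takes one agent and never the other.

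- Under 7.3.2 and 7.4, the patient's events are reported and recorded.
- Under 16.5 as written, the patient does not meet the condition for the safety analysis.
- Under 16.3, no population is named, so nothing there restores the patient.

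The two halves of the document disagree for this patient and agree for everyone who has had both drugs.

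**Step 2: can it happen?** Yes. The two first doses need not coincide, given the free order, outpatient cabozantinib and the 3-day window. Between them, a patient may leave therapy under Section 5.5 for intercurrent illness, an unacceptable adverse event, withdrawal or investigator judgement. It should be uncommon, because both drugs are scheduled for the same day and 6.24 continues cabozantinib after an infusion reaction.

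**Step 3: size.** Let n be the number who received any study drug, k the number who received only one agent, and e the number of both-drug patients with a given event. Suppose all k single-agent patients had that event.

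- Rate in the both-drugs set: e/(n − k)
- Rate in the either-drug set: (e + k)/n
- Understatement: (e + k)/n − e/(n − k) = k(n − k − e)/[n(n − k)]

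This is largest at e = 0, where it equals k/n. The maximum is thus 1/n per patient: 1/35 = 2.9 points or 1/18 = 5.6 points.

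The values n = 35 and n = 18 come from Sections 5.1 and 16.1. The documents give neither k nor e. The table assumes k from 0 to 3 and, for illustration, e = 0 or 5.

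| n | k | e | Both-drugs set | Either-drug set | Understatement (points) |
|---|---|---|---|---|---|
| 18 | 0 | 5 | 5/18 = 27.8% | 5/18 = 27.8% | 0 |
| 18 | 1 | 0 | 0/17 = 0% | 1/18 = 5.6% | 5.6 |
| 18 | 1 | 5 | 5/17 = 29.4% | 6/18 = 33.3% | 3.9 |
| 18 | 3 | 5 | 5/15 = 33.3% | 8/18 = 44.4% | 11.1 |
| 35 | 1 | 0 | 0/34 = 0% | 1/35 = 2.9% | 2.9 |
| 35 | 1 | 5 | 5/34 = 14.7% | 6/35 = 17.1% | 2.4 |
| 35 | 3 | 5 | 5/32 = 15.6% | 8/35 = 22.9% | 7.2 |

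**Step 4: direction.** For an event that the excluded patient did not have, exclusion raises the reported rate, from e/n to e/(n − 1). With e = 5 that is 5/35 = 14.3% to 5/34 = 14.7%, or 5/18 = 27.8% to 5/17 = 29.4%. The understatement applies only to events the excluded patient had.

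**The case against.** The strongest reply is that naming the two drugs together may be loose wording for the regimen. Section 16.5 says whose data will be collected; it does not say in terms that others are excluded, and 16.3 sets no limit. A deliberate exclusion cannot be read into the text. That stands, but it leaves the population ambiguous, and the literal reading is the one a programmer would most naturally implement.

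Three stronger readings are tempting, and the documents do not support them:

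- **A reader might infer that a single-agent patient's events are not counted anywhere.** Sections 7.3.2, 7.4, 7.5 and 7.6 require them to be reported or recorded, and under Section 12.2 the Data and Safety Monitoring Committee reviews toxicity data. What is at risk is their place in the safety summary.
- **A reader might take a Day 1 infusion reaction as the typical route to exclusion.** Section 6.24 continues cabozantinib after every grade of reaction, so a patient managed under that table would normally have both drugs and be in the set. What remains is a patient who stops or is held between the two first doses.
- **A reader might infer a general downward bias.** Step 4 shows that the direction depends on the event. That omitted patients would be those with the most severe early events is plausible but not stated in the documents.

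It is also true that no stated decision depends on this. Stage 2 opens on responses alone, there is no toxicity threshold, and safety is a descriptive endpoint listed as secondary in 16.1.2.

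**Conclusion.** The point holds as a conflict between the analysis text and the collection text. Read literally, 16.5 requires at least one dose of each drug, while 7.3.2 and 7.4 start from the first dose of study treatment. A single-agent patient would have events recorded but left out of the safety summary.

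The effect is probably small. It is at most 2.9 points per patient at n = 35 and 5.6 points per patient at n = 18, for an event that patient had, and it reaches those limits only if no included patient had the same event. With no single-agent patients it is zero. The documents give no expected number, so the range of 0 to 3 is an assumption. The response rule and the stated error rates are unaffected. The correction is still worth making, because it removes a contradiction and a possible toxicity-related exclusion from the only stated basis for judging tolerability.

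**What to change.** In 16.5, replace the 'and' between the two drug names with 'or', so that the safety set is every enrolled patient who took any dose of either agent. State in 16.3 that the toxicity tabulations use this set, and align the collection wording in 16.5 with 7.3.2 and 7.4. It would also help to report how many patients received one agent only, and which one.

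The cost is a one-word change plus a cross-reference. Section 7 already requires the data, so nothing new is collected. Sample size, the response rule and patient management do not change.

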APPENDIX A

PERFORMANCE STATUS CRITERIA

ECOG Performance Status Scale		Karnofsky Performance Scale	
Grade	Descriptions	Percent	Description
0	Normal activity. Fully active, able to carry on all pre-disease performance without restriction.	100	Normal, no complaints, no evidence of disease.
		90	Able to carry on normal activity; minor signs or symptoms of disease.
1	Symptoms, but ambulatory. Restricted in physically strenuous activity, but ambulatory and able to carry out work of a light or sedentary nature (e.g., light housework, office work).	80	Normal activity with effort; some signs or symptoms of disease.
		70	Cares for self, unable to carry on normal activity or to do active work.
2	In bed <50% of the time. Ambulatory and capable of all self-care, but unable to carry out any work activities. Up and about more than 50% of waking hours.	60	Requires occasional assistance, but is able to care for most of his/her needs.
		50	Requires considerable assistance and frequent medical care.
3	In bed >50% of the time. Capable of only limited self-care, confined to bed or chair more than 50% of waking hours.	40	Disabled, requires special care and assistance.
		30	Severely disabled, hospitalization indicated. Death not imminent.
4	100% bedridden. Completely disabled. Cannot carry on any self-care. Totally confined to bed or chair.	20	Very sick, hospitalization indicated. Death not imminent.
		10	Moribund, fatal processes progressing rapidly.
5	Dead.	0	Dead.

APPENDIX B GI ADVERSE EVENT MANAGEMENT ALGORITHM

These general guidelines constitute guidance to the Investigator and may be supplemented by discussions with the Medical Monitor representing the Sponsor. The guidance applies to all immuno-oncology agents and regimens.

A general principle is that differential diagnoses should be diligently evaluated according to standard medical practice. Non-inflammatory etiologies should be considered and appropriately treated.

[figure not shown]
Corticosteroids are a primary therapy for immuno-oncology drug-related adverse events. The oral equivalent of the recommended IV doses may be considered for ambulatory patients with low-grade toxicity. The lower bioavailability of oral corticosteroids should be taken into account when switching to the equivalent dose of oral corticosteroids.

Consultation with a medical or surgical specialist, especially prior to an invasive diagnostic or therapeutic procedure, is recommended.

The frequency and severity of the related adverse events covered by these algorithms will depend on the immuno-oncology agent or regimen being used.

GI Adverse Event Management Algorithm

[figure not shown]
Rule out non-inflammatory causes. If non-inflammatory cause is identified, treat accordingly and continue I-O therapy. Opiates/narcotics may mask symptoms of perforation. Infliximab should not be used in cases of perforation or sepsis.

Patients on IV steroids may be switched to an equivalent dose of oral corticosteroids (e.g. prednisone) at start of tapering or earlier, once sustained clinical improvement is observed. Lower bioavailability of oral corticosteroids should be taken into account when switching to the equivalent dose of oral corticosteroids.

Pulmonary Adverse Event Management Algorithm

[figure not shown]
Rule out non-inflammatory causes. If non-inflammatory cause, treat accordingly and continue I-O therapy. Evaluate with imaging and pulmonary consultation.

Patients on IV steroids may be switched to an equivalent dose of oral corticosteroids (e.g. prednisone) at start of tapering or earlier, once sustained clinical improvement is observed. Lower bioavailability of oral corticosteroids should be taken into account when switching to the equivalent dose of oral corticosteroids

Hepatic Adverse Event Management Algorithm

Rule out non-inflammatory causes. If non-inflammatory cause, treat accordingly and continue I-O therapy. Consider imaging for obstruction.

[figure not shown]

Patients on IV steroids may be switched to an equivalent dose of oral corticosteroids (e.g. prednisone) at start of tapering or earlier, once sustained clinical improvement is observed. Lower bioavailability of oral corticosteroids should be taken into account when switching to the equivalent dose of oral corticosteroids.

*The recommended starting dose for grade 4 hepatitis is 2 mg/kg/day methylprednisolone IV.

Renal Adverse Event Management Algorithm

[figure not shown]
Rule out non-inflammatory causes. If non-inflammatory cause, treat accordingly and continue I-O therapy.

Patients on IV steroids may be switched to an equivalent dose of oral corticosteroids (e.g. prednisone) at start of tapering or earlier, once sustained clinical improvement is observed. Lower bioavailability of oral corticosteroids should be taken into account when switching to the equivalent dose of oral corticosteroids.

Endocrinopathy Adverse Event Management Algorithm

[figure not shown]
Rule out non-inflammatory causes. If non-inflammatory cause, treat accordingly and continue I-O therapy. Consider visual field testing, endocrinology consultation, and imaging.

Patients on IV steroids may be switched to an equivalent dose of oral corticosteroids (e.g. prednisone) at start of tapering or earlier, once sustained clinical improvement is observed. Lower bioavailability of oral corticosteroids should be taken into account when switching to the equivalent dose of oral corticosteroids.

Skin Adverse Event Management Algorithm

Rule out non-inflammatory causes. If non-inflammatory cause, treat accordingly and continue I-O therapy.

[figure not shown]
Patients on IV steroids may be switched to an equivalent dose of oral corticosteroids (e.g. prednisone) at start of tapering or earlier, once sustained clinical improvement is observed. Lower bioavailability of oral corticosteroids should be taken into account when switching to the equivalent dose of oral corticosteroids.

*Refer to NCI CTCAE v4 for term-specific grading criteria.

[^]If SJS/TEN is suspected, withhold I-O therapy and refer patient for specialized care for assessment and treatment. If SJS or TEN is diagnosed, permanently discontinue I-O therapy.

[figure not shown]
Neurological Adverse Event Management Algorithm

Rule out non-inflammatory causes. If non-inflammatory cause, treat accordingly and continue I-O therapy.

Patients on IV steroids may be switched to an equivalent dose of oral corticosteroids (e.g. prednisone) at start of tapering or earlier, once sustained clinical improvement is observed. Lower bioavailability of oral corticosteroids should be taken into account when switching to the equivalent dose of oral corticosteroids.

Myocarditis Adverse Event Management Algorithm

Patients on IV steroids may be switched to an equivalent dose of oral corticosteroids (eg, prednisone) at start of tapering or earlier, once sustained clinical improvement is observed. Lower bioavailability of oral corticosteroids should be taken into account when switching to the equivalent dose of oral corticosteroids.

Prophylactic antibiotics should be considered in the setting of ongoing immunosuppression.

ATG = anti-thymocyte globulin; BNP = B-type natriuretic peptide; ECG = electrocardiogram; IV = intravenous; MRI = magnetic resonance imaging

APPENDIX C BIOSPECIMEN PREPARATION

Processing Guidelines for Tissue Biopsies

1. Five to seven cores will be collected utilizing a 16-18 gauge needle is recommended, a 20 gauge core needle biopsy is also acceptable at the discretion of the interventionalist performing the procedure. Collection of less than the goal amount of tissue will not be considered a protocol violation and should be based upon the clinical judgement of the clinician performing the biopsy procedure.
2. Tissue mass is placed on a sterile saline soaked Telpa pad
3. Using forceps or scalpel, tumor tissue is separated into multiple fragments, if necessary
4. Distinct tissue fragments will be allocated for the following, in order of protocol priority:
 - a. Two to three samples placed in room temperature formalin for processing to a FFPE block to be set to the DFCI [name] Lab.
 - b. One sample placed in room temperature formalin to be set to BWH Pathology per BWH CSIR SOP.
 - c. Two to three samples placed in room temperature formalin for processing to additional FFPE block(s) to be stored by the DFCI Clinical Trials Team ([name]).
5. Samples will be annotated with only a unique de-identified study subject number, protocol number, and the date of collection. Links to identifying information for each sample will be stored centrally on a password-protected firewall secured database in accordance with institution tissue bank protocols.

Processing Guidelines for Whole Blood and Plasma Samples

1. Samples will be collected as follows:
 - a. Green Top 10 ml Sodium Heparin Tubes for PBMCs
2. Samples will be delivered immediately to the CIO Immune Assessment Lab to be processed within 1.5 hours of being drawn.

CIO Immune Assessment Lab of [name]:

Center for Immuno-Oncology
Dana-Farber Cancer Institute
[name]
[name]
[contact]
[name]

Processing Guidelines for Stool Samples

1. Samples will be collected per kit instructions.
2. Samples will be delivered immediately to the CIO Immune Assessment Lab to be processed.

CIO Immune Assessment Lab of [name]:

Center for Immuno-Oncology
Dana-Farber Cancer Institute
[name]
[name]
[contact]
[name]

APPENDIX D MULTI-CENTER GUIDELINES

APPENDIX D

**Dana-Farber/Harvard Cancer Center
Multi-Center Data and Safety Monitoring Plan**

